The adjudication committee will evaluate patients who are deemed by site investigators to meet this endpoint (severe bleeding or clotting) in batches of 5 patients. The adjudicators will rotate, which will help prevent bias and ensure that all adjudicators have an equal opportunity to contribute to the study. We will report the inter-rater reliability (Kappa) at the end of the study. The committee will make determinations for whether bleeding was the primary cause of the worsening clinical outcome or if clotting was severe. Specifically, the sites will complete the severe bleeding/clotting daily worksheet (see Appendix E) on a daily basis. If a severe bleeding event, or clotting event, the event will be recorded in the database (and the intervention will stop for that participant since this safety outcome has been reached). Once five new patients have any of these events reported, the adjudication committee will review the events and report if they agree with the determination of the outcome within 72 hours of their review or if they need additional information from the site PI. Patient enrollment will continue during their reviews.

B. Secondary Outcomes

Our second objective is to demonstrate the ability for observed endpoints to satisfy various prespecified feasibility thresholds. The information the pilot trial will provide is both necessary and sufficient for the implementation of the full clinical trial. Based on PALISI and BloodNet's suggestions, we will seek further funding and progress to the full trial if at least 5 of the following 10 criteria are met:

- 1. Estimated separation in mean pre-transfusion platelet count is $> 30 \times 10^9$ cell/L;
- 2. Eligibility rate is > 50% of the predicted eligibility rate of 7.9 patients per site per year;
- Proportion of patients whose parents were approached for consent within 24 hours of cannulation (number of patients approached / number of patients eligible for consent) > 90%;
- Proportion of patients for whom we were able to obtain informed consent (number of patients consented / number of patients approached) > 50%;
- 5. Randomization of consented patients is > 66%;

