- We will optimize and document the ability to adjudicate a *bleeding and/or thrombotic outcomes* using both the BASIC and NHLBI developed definitions.
- *Eligibility numbers and enrollment rates* will inform the number of centers, size of centers (high volume versus low volume), and location of centers (US-only versus international) required to accrue the required sample size for the subsequent ECSTATIC RCT.
- We will document the ability to enroll patients through standard consent, which will allow us to determine if an Exception From Informed Consent (EFIC) will be needed for the larger RCT. This finding will also contribute to the selection of sites for the larger RCT as some countries have no provision for EFIC.
- *Protocol deviations*, should they occur in the pilot trial, will provide opportunities to refine key protocol elements, including reasons for protocol suspension, in order to maximize protocol adherence and minimize risk of bias in the subsequent ECSTATIC RCT.
- We will document and classify *temporary suspensions* to allow for refinement in the subsequent RCT.

10. Sample Size and Statistical Analysis

A. Sample Size

Salient assumptions to permit power estimation include the number of observed transfusion days per subject, the within-subject dependence structure, the within-treatment variability, and the difference in means between treatments. Previous data, albeit not with an enforced low platelet threshold transfusion strategy, were used to inform the first three assumptions. It was assumed the distribution of the number of transfusion days per subject will mimic historical data (e.g., approximately 10%-20% will have no transfusions). It was assumed a compound symmetry covariance structure will adequately account for within-subject dependence; such a structure is induced by a mixed effects model with subject-specific random intercepts. Fitting a model with such a covariance structure to historical data [6] yielded an estimated autocorrelation slightly above 0.2; to be conservative the power estimation assumed ρ =0.3 (6). The assumed within-treatment standard deviation, 40x10⁹/L, resembles historical data but is anticipated to be a conservative estimate for the trial.

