Although the difference in platelet strategy thresholds is $40x10^{9}/L$ (i.e., $90 \times 10^{9}/L \times 50 \times 10^{9}/L$), this full effect will not be realized for the mean difference because the strategies depend on platelet counts which are not continuously observed, and as such, by the time of measurement a patient may have a platelet count considerably below the threshold. Patients with a platelet count

under 50 x10⁹/L would be transfused under either strategy. Therefore, a more realistic separation for the difference in means between strategies is 30 x10⁹/L.

Assuming pre-transfusion platelet levels will be approximately normally distributed with a difference in means of 30×10^{9} /L, then with **50 patients (25 per arm)** enrolled there would be approximately **81% power** to detect a difference in mean platelet levels at the time of transfusion. Power may be higher due to conservative assumptions.

The design of the *full RCT*, which will test the non-inferiority of a low platelet threshold strategy, will be informed by the separation in pre-transfusion platelet counts in both arms, median number of transfusions in each group, proportion of patients who develop the primary safety outcome (progression to severe bleeding and/or severe thrombotic event and/or study-related death) or tertiary outcome (progression to severe bleeding and/or severe thrombotic event), proportion of patients who require temporary suspension, proportion of patients with non-platelet transfusion protocol violations, and the consent rate.

B. Planned Recruitment Rate

There is a wide heterogeneity in the number of ECMO runs per center and per year. The sum of the eligible patients from the ten centers who have committed to participate in the pilot trial is 79 patients per year. We therefore would require an enrollment rate of 32% to recruit all of the patients within 24 months [50 patients / (2 years x 79 patients per year) = 0.32]. As a result, we are very confident we will complete the pilot trial within 3 years.

All the participating sites have at least 10 ECMO runs per year (the larger sites have up to 50 a year). Therefore, we anticipate that even the smaller sites should be able to enroll 5 patients over 18 months. However, should the enrollment be slower than expected, we will lift the cap on the larger sites (currently set at 10 subjects).

C. Statistical Analysis

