This will be a multicenter, non-inferiority, randomized, controlled, investigator-initiated, open-label, trial with blinded adjudication of the outcomes (Figure 10). We will take into account the recommendations of SPIRIT to elaborate our final version of the protocol for the full ECSTATIC RCT (57). We will use the PRECIS-2 tool to estimate the pragmatic or explanatory nature of the trial (58).

Site Eligibility

PICUs will be considered eligible to participate in the full ECSTATIC RCT only if there is an ECMO program in the site.

Site Inclusion Criteria: Pediatric and neonatal ICUs, including cardiac PICUs, with at least a mean of 5 ECMO runs per year.

Site Exclusion Criteria: PICUs will be excluded if 1) a consensus from all physicians working in the PICU to apply the research protocol is not reached, and/or 2) if there is no local scientific infrastructure that can support the participation in a large multicenter RCT.

Patient Eligibility

Children will be eligible if admitted to a participating tertiary care PICU, NICU or CICU for whom the decision to cannulate for ECMO support has been made.

Inclusion Criteria: Critically ill children (0 to <18 years of age), admitted to a participating PICU/NICU/CICU, on ECMO for less than 24 hours, and who have either no bleeding or minimal bleeding. If a patient experiences more than minimal bleeding after ECMO

ECMO Hemostatic Transfusions in Children (ECSTATIC) Study Protocol – version 1.4 – April 22, 2024

cannulation, they can be enrolled once bleeding meets criteria for no/minimal bleeding, with the condition that the moderate or severe bleeding resolves within the first 24 hours of ECMO initiation.

Exclusion Criteria

To ensure our trial is as **pragmatic** as possible, we have as few exclusion criteria as possible:

- 1) post conception age < 37 weeks at time of screening
- 2) underlying oncologic diagnosis (defined as receipt of chemotherapy or radiation in the last six months) or recipient of bone marrow transplant in the last year
- 3) congenital bleeding disorder or congenital thrombocytopenia
- 4) pregnant or admitted post-partum (within 6 weeks of giving birth)
- 5) decision to withdraw or withhold some critical care or interventions
- 6) known objection to blood transfusions
- 7) on ECMO for > 24 hours at time of enrollment

Inclusion criteria and exclusion criteria will be ascertained by pediatric critical care clinical or research staff.

Intervention

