If non-inferiority were not demonstrated, experts believe such trials still provide important information, since we will be able to report multiple secondary and tertiary outcomes, such as blood product exposure and lengths of ECMO or stay. Such results would still be impactful, as a potential decrease in blood product exposure or in lengths of care would be clinically meaningful.

In terms of feasibility, enrolling 1238 patients in 30 centers who would each enroll 10 subjects by year, would require just over 4 years.

Statistical Analyses

The analysis of the primary outcome measure will be conducted on an **intention to treat** (ITT) basis for all patients randomized in ECSTATIC. The principal analysis, i.e., the influence of platelet transfusion strategy ("higher platelet threshold" vs. "lower platelet threshold") on the primary outcome (progression to severe bleeding and/or severe clotting, ignoring such events that begin during a period of temporary suspension), will be done using an unadjusted z-test (with continuity correction) of non-inferiority, comparing the proportion of patients who progress to the primary outcome after randomization in both groups. The principal effect measure will be an unadjusted absolute risk reduction (ARR) with a 95% CI for the primary comparison.

Secondary analyses of the primary composite outcome will include logistic regression modeling to further elucidate the measure of effect while adjusting for known prognostic risk factors. For adjusted models, risk factors such as site, age, co-morbid illnesses, type of ECMO, indication to ECMO, and severity of illness scores will be added based on clinical (not statistical) rationale. Continuous risk factors (e.g., PELOD-2, number of transfusions) will be entered into the models as a continuous measure to improve statistical efficiency. Regression diagnostics will be performed on all models. We will also compare Kaplan-Meier curves using a log rank test followed by proportional hazards modeling for liberation from ECMO alive, 28- and 90-day mortality, and time to the composite outcome: these analyses will compare the length of time between randomization and appearance of those outcomes.

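### Does the full-trial projection in Appendix A need correcting because its 10 enrolled per center-year exceeds the 7.9 eligible per site-year counted for the pilot?

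*Combined protocol and SAP*

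**What the plan says.** The protocol's Appendix A outlines a possible later non-inferiority trial of 1238 patients. Its Sample Size section ends with a feasibility sentence: "enrolling 1238 patients in 30 centers who would each enroll 10 subjects by year, would require just over 4 years". No source is given for 10 per center-year. Under Site Eligibility, the same appendix admits pediatric and neonatal intensive care units "with at least a mean of 5 ECMO runs per year".

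The pilot's recruitment figures are in section 10.B. "The sum of the eligible patients from the ten centers who have committed to participate in the pilot trial is 79 patients per year", and "We therefore would require an enrollment rate of 32% to recruit all of the patients within 24 months". The same section notes wide variation in volume: every site has at least 10 ECMO runs a year and the larger ones up to 50. It expects even smaller sites to enroll 5 patients in 18 months. The average of 7.9 reappears in section 9.B as feasibility criterion 2 ("Eligibility rate is > 50% of the predicted eligibility rate of 7.9 patients per site per year") and in SAP 2.2.2 as SE2.

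Section 9.E describes how the pilot feeds the later trial. What the pilot observes about eligibility and accrual "will inform the number of centers, size of centers (high volume versus low volume), and location of centers (US-only versus international").

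**The concern.** Read together, these figures seem to contradict one another. A center cannot enroll more children than are eligible there, yet the projection has each of 30 centers enrolling 10 a year when the average pilot site has 7.9 eligible. A unit at the entry floor of 5 runs a year could not reach 10 even if it enrolled every run.

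The pilot exists to judge whether the full trial is feasible, and this sentence is the documents' only statement of how many centers and years that trial would take. If it were used as it stands to fix the number of centers, the full trial could be started with too few sites and run well past its planned end.

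**Working it through.** **Inputs.** Appendix A: N = 1238, 30 centers, 10 per center-year. Section 10.B: 79 eligible a year at ten sites; 50 patients in 2 years; 5 patients in 18 months at smaller sites; 10 to 50 runs per site-year. Appendix A, Site Eligibility: floor of 5 runs a year.

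**The plan's own figures.**
- Sample size: event rates 65% and 60.7%, margin 5%, one-sided alpha 0.025, power 90%. The distance to the margin is 0.05 + 0.043 = 0.093. The unpooled formula gives 566.2 per arm, and the continuity correction raises this to 587.5, rounded up to 588. Allowing for 5% drop-out, 588/0.95 = 618.9, so 619 per arm and 1238 in total. This matches.
- Duration: 1238/(30 × 10) = 4.13 years. This matches.

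**The input against the pilot's counts.**
- Average eligible: 79/10 = 7.9 per site-year. Ratio: 10/7.9 = 1.27.
- Thirty average sites: 30 × 7.9 = 237 eligible a year, against 30 × 10 = 300 to be enrolled.
- A unit at the floor: 10/5 = 200% of its runs.

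**Duration with 30 centers like the pilot's and static volume** (years = 1238/(30 × rate)).

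| Rate per site-year | Basis | Years |
|---|---|---|
| 10 | Appendix A | 4.13 |
| 7.9 | every eligible child enrolled | 1238/237 = 5.2 |
| 5/1.5 = 3.33 | section 10.B, smaller sites | 1238/100 = 12.4 |

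At 7.9 per site-year, keeping 4.13 years would take 300/7.9 = 38 centers.

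**Whether 10 is out of reach.** The 7.9 is a mean over ten sites of very different size. A center with 50 runs would reach 10 by enrolling 10/50 = 20% of its runs. Section 5.A reports worldwide case growth of 5 to 10% a year. If per-center eligibility grew at that pace (an assumption), 7.9 would reach 10 in ln(10/7.9)/ln(1.10) = 2.5 years to ln(10/7.9)/ln(1.05) = 4.8 years; section 11.D gives the pilot three years. The documents therefore show 10 to be unsupported, not unattainable.

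**Whether the pilot supplies the replacement figure.** SAP 2.2.2 defines SE2 from eligible patients per site-year open, SE3 as approached/eligible, SE4 as consented/approached and SE5 as randomized/consented. The product of the observed SE2 rate and the three proportions is randomized patients per site-year open. SAP 7.3.1 has each of these quantities reported, so planners will have the observed accrual rate without any new analysis.

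**Whether the pilot uses the 10.** It does not enter the pilot's sample size of 50, the mixed model, the safety stopping rule or any of the ten feasibility criteria. Criterion 2 is tied to 7.9.

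**The case for a change.** The best case for a change is that feasibility of the full trial is the pilot's stated purpose, so its one accrual projection should agree with the protocol's own counts. The floor of 5 runs and the 10 enrolled by each center stand in the same appendix, so that conflict does not depend on future sites resembling pilot sites. Exception from informed consent, raised in section 9.E, could increase the share enrolled but not the number eligible. Section 9.E also gives no formula for turning pilot rates into a number of centers. One clause would repair the text.

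Part of this stands. No basis is given for 10, it exceeds the pilot average, and a center at the floor could not meet it. The rest is weaker:

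- An entry floor is not an expected volume. It is written for intensive care units, while the projection counts centers, and section 6.B shows that a site may contain NICU, PICU and CICU.
- A harsher projection is available from the pilot's target of 50/(10 × 2) = 2.5 per site-year, which gives 1238/(30 × 2.5) = 16.5 years. That rate is fixed by the pilot's size, its window and its cap of 10 per center. It is not a forecast of what sites can do, and section 10.B itself expects more (3.33) even from smaller sites.
- The missing formula is a gap that any analyst planning the next trial would fill from the reported SE2 to SE5 quantities, looking at high- and low-volume sites separately as section 9.E anticipates.

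**Conclusion.** No change is needed. The sentence is arithmetically correct and conditional on a visible input. That input is optimistic: with a pilot-like site mix and static volume, 30 centers would take at least 5.2 years, and about 12.4 years at the pace expected of smaller sites, rather than 4.1. Those longer figures rest on the provisional 1238 and on future centers resembling the ten pilot sites, which the documents do not say.

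Section 5.D confines the protocol to the pilot. Appendix A is a proposal that calls the data behind its own sample size very uncertain, and section 9.E already leaves the number, size and location of centers to be informed by what the pilot observes. Rewriting the sentence would alter nothing the pilot does to its participants, analyzes or can conclude. Following the plan as written still puts the observed accrual rate in front of whoever sizes the full trial, and that rate, not the 10, should be used then.

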1 PREFACE

Purpose of SAP 1.1

This Statistical Analysis Plan (SAP) describes the planned analysis and reporting for the protocol: ECMO Hemostatic Transfusions in Children.

The structure and content of this SAP provides sufficient detail to meet the requirements and standards set by the Data Coordinating Center (DCC).

1.2Auxiliary/Other Documents

The following documents were reviewed in preparation of this SAP:

- Protocol: ECMO Hemostatic Transfusions in Children.
- Case Report Forms (CRFs) for the ECSTATIC protocol

The reader of this SAP is encouraged to read the protocol for details on the conduct of this study, and the operational aspects of clinical assessments.

The purpose of this SAP is to outline the planned analyses to be completed for the EC-STATIC trial. The planned analyses identified in this SAP will be included in future study abstracts and manuscripts. Also, exploratory analyses not necessarily identified in this SAP may be performed. Any post hoc, or unplanned, analyses not explicitly identified in this SAP will be clearly identified as such in any published reports from this study.

It is possible that, due to updates or identification of errors in specific statistical software discussed in this SAP, the exact technical specifications for carrying out a given analysis may be modified. This is considered acceptable as long as the original, prespecified statistical analytic approach is completely followed in the revised technical specifications.

STUDY OBJECTIVES AND OUTCOMES 2

Study Objectives 2.1

Primary Objective(s) 2.1.1

The primary objectives of the ECSTATIC trial are:

Page 1

- Aim 1: to demonstrate a separation between the LOWER and HIGHER platelet threshold transfusion arms. Specifically, we will demonstrate a difference in the average pre-transfusion platelet count between the two arms from randomization to when the treatment strategy was permanently discontinued. In addition, we will estimate the difference in average daily platelet dose during the same period, which we anticipate will be a difference of at least 20% between the groups randomized to each threshold.
- Aim 2: to demonstrate the ability for observed endpoints to satisfy various prespecified feasibility thresholds. Specifically, there are 10 different criteria and we will show that at least 5 of the 10 thresholds are satisfied by the estimated endpoints.
- Aim 3: to provide additional information on the epidemiology of a novel composite outcome of progression to severe bleeding and/or severe thrombosis, to incorporate in the design of the full RCT. Specifically, we will demonstrate that the estimated rate of adjudication by an independent panel is more than 90% of the enrolled subjects for whom the outcome was reported by the site as having occurred.

2.2 Study Outcomes

2.2.1 Primary Outcome(s)

The **primary outcome for Aim 1**, hereafter *primary outcome*, is the platelet count immediately (or as recently as available) before a transfusion. Note that this outcome is defined for each transfusion, and as such, participants may contribute multiple values.

Though not considered primary outcomes, there are two outcomes that are especially related to the primary outcome which are of additional interest: the total platelet transfusion dose while on ECMO in mL/kg/run, and the transfusion dose in mL/kg/hr (or its redundant value, in mL/kg/day, obtained by multiplying the dose in mL/kg/hr by 24). Refer to Section 5.5 for details of the mL/kg/run and mL/kg/hr calculations.

For safety monitoring, there is a **primary safety outcome**, (occurrence of progression to severe bleeding, severe thrombosis, or death, in the acute follow-up period more precisely defined in Section 2.2.5). To avoid confusion, any reference to the primary safety outcome contains the qualifier "safety."

2.2.2 Secondary Outcome(s)

The secondary endpoints (SEs) are: observed values of estimated separation in mean pretransfusion platelet counts; eligibility rate relative to predicted rate; approach for consent percentage; consent percentage; randomization of consented patients percentage; transfusion compliance rate; transfusion strategy suspension percentage; withdrawal and or lostto-follow-up percentage; violation of local non-study-specific circulatory support protocol percentage; and adjudication rate of progression to severe bleeding/thrombotic outcomes.

Each endpoint is based on an underlying outcome and has an associated feasibility threshold. **To support a larger trial, at least five out of ten feasibility criteria must be met.** The underlying outcomes and thresholds for these 10 secondary endpoints (SE1–SE10) criteria are defined in the next paragraphs.

(SE1) Estimated separation in pre-transfusion platelet counts

- \bullet Outcome: Uses the primary outcome, pre-transfusion platelet count, defined in Section 2.2.1
- Endpoint: Model-based estimated effect of transfusion strategy; see Section 7.2 for modeling details
- Feasibility threshold: Model-based estimated difference $> 30 \times 10^9$ cells/L

(SE2) Eligibility rate relative to predicted eligibility rate

- Outcome: For each patient screened (see definition in Section 4.2.1), it will be determined whether the patient was indicated in the study database as meeting all study eligibility criteria, did not meet all study eligibility criteria, or whether screening was indeterminate
- Endpoint: The observed eligibility rate as a percentage of the predicted eligibility rate. That is,

$$100\% \times \frac{\text{observed eligibility rate}}{\text{predicted eligibility rate}},$$

where the predicted eligibility rate is 7.9 patients per site per year, and the observed eligibility rate per site per year will be calculated as (# in ELIGIBLE population)/(total # of site-years enrollment was open). The ELIGIBLE population is defined in Section 4.2.3. For each site, the enrollment duration is the number of calendar days from the site being activated for enrollment to the site being closed to enrollment, inclusive, divided by 365.25 (approximate # of days per year)

• Feasibility threshold: > 50%

(SE3) Approach for consent percentage

• Outcome: For each patient in the ELIGIBLE population (see Section 4.2.3), whether the patient was in the APPROACHED population (approached for study participation within 24 hours of cannulation; see also Section 4.2.4)

- Endpoint: $100\% \times (\# \text{ in APPROACHED population}) / (\# \text{ in ELIGIBLE population})$
- Feasibility threshold: > 90%

(SE4) Consent percentage

- Outcome: For each patient in the APPROACHED population (see Section 4.2.4), whether the person was consented to study participation (see also Section 4.2.5 for a description of the CONSENTED population)
- Endpoint: 100% \times (# in CONSENTED population) / (# in APPROACHED population)
- Feasibility threshold: > 50%

(SE5) Randomization of consented patients percentage

- Outcome: For each patient in the CONSENTED population, whether the person was in the ITT population (i.e., consented and randomized; equivalently, in the ENROLLED population; see Section 4.2.6)
- Endpoint: $100\% \times (\# \text{ in ITT population}) / (\# \text{ in CONSENTED population})$
- Feasibility threshold: > 66% (previous data indicate approximately one-third of patients bleed within 24 hours of cannulation)

(SE6) Transfusion compliance rate

• Outcome: This is a transfusion-level outcome for the ITT population, such that some patients could have multiple outcomes and others could have no outcomes. Any transfusions that were performed under a period of temporary suspension will be ignored. Among the remaining transfusions performed between randomization and when the treatment strategy was permanently discontinued, the transfusion will be considered compliant if and only if (a) the most recent nonmissing pre-transfusion platelet count (obtained no more than 12 hours before the transfusion, and not obtained prior to an earlier transfusion) was below the assigned threshold AND (b) the site principal investigators agree the transfusion dose was the proper dose in use at the site (e.g., 10 mL/kg if that is the local guideline and the same guideline applies to each arm of the study); if the pre-transfusion platelet count is not available, it will be assumed that the transfusion was not compliant. Also, if a transfusion was indicated per the threshold (i.e., the platelet count was below the threshold) but no transfusion was given within 12 hours, this will also be considered as an outcome and automatically be regarded as noncompliance

- Endpoint: 100% × (# of compliant transfusions not during a temporary suspension)/ (# of transfusions not during a temporary suspension + number of transfusions that should have been given but were not)
- Feasibility threshold: >90%

(SE7) Transfusion strategy suspension (not due to preparation for decannulation) percentage

- Outcome: For each patient in the ITT population (see Section 4.2.6), whether the patient had at least one temporary suspension of the transfusion threshold not due to preparation for decannulation before the permanent discontinuation of the treatment strategy. A temporary suspension of the transfusion threshold will not require a transfusion in excess of the threshold to have been given during the suspension period for it to be counted as a suspension
- Endpoint: $100\% \times (\# \text{ in ITT population with at least one temporary suspension of the transfusion threshold not due to preparation for decannulation) / (# in ITT population)$
- Feasibility threshold: < 10%

(SE8) Withdrawal and/or lost-to-follow-up percentage

- Outcome: For each patient in the ITT population, whether the patient was withdrawn from study participation by 90 days post-randomization and/or had an unknown mortality status for the timepoint of 90 days after randomization. The 90-day vital status will be considered known if the 90-day communication for mortality assessment is completed within ± 10 days, inclusive, of 90 days after randomization, or if the patient was known to have already died (e.g., died while on ECMO) such that the 90-day follow-up mortality assessment is unnecessary
- Endpoint: $100\% \times (\# \text{ in ITT population who were withdrawn from the study by 90 days after randomization or had unknown 90-day mortality) / (# in ITT population)$
- Feasibility threshold: < 6%

(SE9) Percentage with any violations of local non-study-specific circulatory support protocols

• Outcome: For each patient in the ITT population, whether the patient had any reported instances of non-adherence to the site's non-study-specific circulatory support strategies. For this outcome, any instances of platelet transfusions above the randomized threshold are immaterial; on the other hand, for example, if the anticoagulation

strategy in place at the site was not followed, this is considered a protocol violation for this outcome. The site PIs will determine whether or not local protocols were followed

- Endpoint: $100\% \times (\# \text{ of ITT patients with any reported violations of local non-study-specific circulatory support protocols)/(# of ITT patients)$
- Feasibility threshold: < 5%

(SE10) Adjudication percentage of progression to severe bleeding/thrombotic outcomes

- Outcome: This is defined for each patient in the ITT population (Section 4.2.6) for whom there was any site-reported instance of progression to severe bleeding and/or thrombosis in the acute follow-up period (the **acute follow-up period** consists of the time from randomization through 24 hours past when the transfusion strategy was last applicable). Because any site-reported severe bleeding or severe prognosis is cause to terminate use of the transfusion strategy for that patient, we focus on whether the initial such event can be adjudicated, whether or not additional distinct events were later observed. The patient's outcome is defined as adjudicated if the adjudication panel reached a decision for the initial site-reported event (confirming or overturning the site-level decision for the initial event), and defined as not adjudicated if the panel was unable to reach either a confirmation or overturning decision for the reported event even after requesting additional information from the site
- Endpoint: $100\% \times (\# \text{ of ITT patients with site-reported severe bleeding/thrombotic outcomes for which the adjudication panel was able to adjudicate the patient's first such reported outcome)/(# of ITT patients with site-reported severe bleeding/thrombotic outcomes)$
- Feasibility threshold: > 90%

